## 4.10. Safety Data

### 4.10.1. Adverse Events

Adverse events (AEs) will be coded using MedDRA Version 19.1.

All AEs will be listed and will include but not necessarily be limited to the following: verbatim term, MedDRA preferred term, treatment group, severity, relationship to study medication, action taken with respect to study medication, and whether or not the AE is treatment-emergent although not necessarily in that order.

Treatment-emergent AEs (TEAEs) are defined those AEs that start or worsen in intensity on or after the first study drug administration up to the end of the follow-up period (Day 141 [Part 1] / Day 393 [Part 2]). AEs classified as TEAEs will be summarized. Planned summaries include the following (for each muscle group unless otherwise specified):

- Overall summary of TEAEs by treatment group
- Summary of TEAEs by MedDRA System Organ Class and Preferred Term for each treatment group – Number of Patients

- Summary of TEAEs by MedDRA System Organ Class and Preferred Term for each treatment group – Number of Events
- Summary of TEAEs by MedDRA Preferred Term for each treatment group – Number of Patients
- Summary of TEAEs by MedDRA Preferred Term for each treatment group – Number of Events
- Summary of CTCAE Grade 3 or Higher TEAEs by MedDRA System Organ Class and Preferred Term for each treatment group – Number of Patients
- Summary of CTCAE Grade 3 or Higher TEAEs by MedDRA System Organ Class and Preferred Term for each treatment group – Number of Events
- Summary of CTCAE Grade 3 or Higher TEAEs by MedDRA Preferred Term for each treatment group – Number of Patients
- Summary of CTCAE Grade 3 or Higher TEAEs by MedDRA Preferred Term for each treatment group – Number of Events
- Summary of TEAEs possibly or probably related to study drug by MedDRA System Organ Class and Preferred Term for each treatment group – Number of Patients
- Summary of TEAEs possibly or probably related to study drug by MedDRA System Organ Class and Preferred Term for each treatment group – Number of Events
- Summary of TEAEs possibly or probably related to study drug by MedDRA Preferred Term for each treatment group – Number of Patients
- Summary of TEAEs possibly or probably related to study drug by MedDRA Preferred Term for each treatment group – Number of Events
- Summary of TEAEs by MedDRA Preferred Term by CTCAE Grade and Relationship to Drug for each treatment group – Number of Patients
- Summary of TEAEs by MedDRA Preferred Term by CTCAE Grade and Relationship to Drug for each treatment group – Number of Events
- Summary of Serious Adverse Events – Number of Patients

#### 4.10.2. Clinical Laboratory Evaluations

Individual clinical laboratory data will be listed.

The following table lists the planned clinical laboratory assessments:

Type of Assessment	Details
Hematology	Hemoglobin, hematocrit, platelet count, red blood cell count, white blood cell (WBC) count, and WBC differential
Chemistry	AST, ALT, lactate dehydrogenase (LDH) and isoenzymes 1-5, gamma-glutamyl transpeptidase (GGT), blood urea nitrogen (BUN), creatinine, creatine kinase (CK), myoglobin, aldolase, sodium, potassium, glucose, albumin, total bilirubin
Urine	Urinalysis by dipstick analysis (pH, specific gravity, protein, myoglobin, glucose, ketones, blood, leukocyte esterase, and nitrite)

In addition to the tests listed below, a urine pregnancy test is performed on all females of childbearing potential according to scheduled times listed in the protocol.

Descriptive statistics of raw data and change from baseline data will be provided by treatment group for each scheduled time.

Plots of mean  $\pm$  SEM will be provided for raw data and change from baseline data for the following selected laboratory data: hemoglobin, glucose, aldolase, blood urea nitrogen (BUN), creatinine kinase (CK), creatinine, and myoglobin.

Additional analyses may be performed as appropriate.

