10.2. Safety Review Team

Dose-Limiting Toxicity (DLT) Definition:

• An SAE, possibly or probably related to study drug

OR

• An AE, injection site reaction, laboratory parameter abnormality, or vital sign abnormality, possibly or probably related to study drug, and either Grade ≥ 3 (NCI-CTCAE, current version) or Grade ≥ 2 and considered clinically significant

Part 1 Dose Escalation Stopping Rules (under SRT review):

Dosing at current levels will continue unless the following condition occurs:

• ≥ 2 DLTs of the same character in a cohort

Safety Review Team:

An SRT, comprised at minimum of a principal investigator, medical monitor, and an independent neuromuscular specialist, will meet to review safety and, as needed, imaging data, for each cohort. The review will include all collected safety data (and, as necessary imaging data) when at least 4 patients in a cohort have completed at least their Day 22 visit. For both parts of the study, the SRT safety data will include, but not be limited to, AEs, laboratory results (including hematology, chemistry, and urinalysis) and vital signs data to assess for DLTs and overall safety. The SRT may request review of additional data collected in currently enrolled patients.

Based on review of relevant data, the SRT will make one or more of the following recommendations:

- Continue enrollment of remaining patients in the current cohort at the current dose level
- Open next cohort in Part 1 or open Part 2 of the study at a recommended dose (higher or lower dose level)
- Discontinue one or more cohorts in Part 1, or the study as a whole

SRT recommendations for dose escalation in Part 1 will be based in part upon the dose escalation stopping rules. If a stopping rule is met, a lower intermediate dose may be recommended or the previous dose level will be considered the MTD. The SRT may also recommend no further enrollment in the presence of AEs that do not meet dose stopping rules if the nature of these AEs is deemed a significant risk to patients in a given cohort.

For Part 2, the SRT will review blinded preliminary safety data. Further details on the role of the SRT during Part 2 are included in the SRT Guidelines.

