13. SAFETY

13.1. Definition of Adverse Events

13.1.1. Adverse Event

For this protocol, an AE is any untoward medical occurrence in a clinical investigational study in which a patient is administered a study drug (i.e., on or after the Dose 1 Day 1 dose), which does not necessarily have a causal relationship with this treatment. An AE can therefore be any unfavorable and unintended sign (including an abnormal laboratory finding), symptom, or disease temporally associated with the use of the study drug whether or not it is considered related to the study drug.

Abnormal laboratory and other abnormal investigational findings (e.g., physical exam, ECG) should not be reported as AEs unless they are associated with clinical signs and symptoms, lead to treatment discontinuation, or are otherwise considered clinically relevant by the investigator. In cases of surgical or diagnostic procedures, the condition/illness leading to such a procedure is considered as the AE rather than the procedure itself. In the case of a fatality, the cause of death is considered as the AE, and the death is considered as its outcome.

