14.2.5. Safety Data

Unless otherwise specified, safety data will be summarized using descriptive statistics and individual safety data will be listed. AEs will be coded using the Medical Dictionary for Regulatory Activities. Incidence of treatment-emergent AEs will be presented by system organ class and preferred term. AE incidence rates will be described by cohort with and without regard to causality. The frequency of occurrence of overall toxicity, categorized by toxicity grades (NCI-CTCAE, current version) will be summarized. Change from baseline in clinical laboratory parameters, ECG, and vital signs will be summarized across time. Shift tables will be presented for selected laboratory parameters and vital signs. Physical examination results will be presented in listings.

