### 4.1.5. Data Handling Conventions

Unless otherwise stated or indicated:

- Individual data for all patients will be presented in data listings, sorted by “Study Part” (Part 1 or Part 2), “Treatment Group”, and “Patient Number”;
- For any parameter analyzed, only observations from visits and/or time points planned in the protocol will be used in descriptive statistics. An exception to this rule is for a baseline assessment. Should an unscheduled assessment be taken after the scheduled baseline assessment but before the first dose of study medication, then the unscheduled assessment may be used as the baseline;
- For variables where the Day 1 assessment is defined as the baseline, should an individual patient have a Day 1 assessment after having received their first dose, then an unscheduled assessment may be used as the baseline, provided that the unscheduled assessment was done prior to first dose.
- Should a patient be assigned to the wrong CMT-type stratum (e.g. a CMT1 patient assigned to the CMTX stratum or a CMTX patient assigned to the CMT1 stratum), the patient’s true CMT-type (CMT1 or CMTX) will be used in statistical models where CMT-type is used as a covariate.
- With the exception of what is described in the preceding bullet, unscheduled assessments will not be collectively summarized in summary tables or figures; however, these data will appear in individual patient listings.
- For adverse events where the assessment of “Relationship to study drug” is missing, it will be assumed that the adverse event is “Probably Related” to study drug.
- For selected pharmacodynamic and efficacy data, tests of statistical hypotheses and estimation using the end-of-treatment visit or the Day 190 visit (Part 2 double-blind component), multiple imputation for missing data will be performed. Additional techniques for handling missing data may also be considered and evaluated.
- If a patient has a Day 190 assessment performed after having received the Day 190 dose (first dose in the open-label phase), then the Day 190 assessment for that patient will be included in statistical analyses of Day 190 data only if the difference between the Day 190 assessment and the Day 190 dose date is less than or equal to 7 days.
- Descriptive statistics for quantitative parameters will be provided using number of observations (N), mean, standard deviation (SD), standard error of the mean (SEM), median, minimum and maximum;

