#### Vital Signs

Individual vital sign data will be listed.

Vital sign parameters consist of weight, heart rate, systolic and diastolic blood pressure.

Descriptive statistics will be provided for raw data and absolute change from baseline by scheduled time for each treatment group. Post-dose recheck values will not be used for calculation of descriptive statistics.

Additional analyses may be performed as appropriate.

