#### **4.10.4. Other Safety Data**

Not applicable.

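### The SAP omits, without declaring it, the protocol's shift tables for laboratory values and vital signs, so no planned table counts patients who move to an abnormal or worse category

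*SAP*

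**What the plan says.** Protocol 14.2.5 plans two separate outputs for laboratory values and vital signs. One is change from baseline over time. The other is shift tables: "Shift tables will be presented for selected laboratory parameters and vital signs". The synopsis makes the same commitment for Part 1 and carries Part 1's safety analysis over to Part 2.

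The SAP keeps the first output only. For laboratory data (SAP 4.10.2) it plans listings, mean and SEM plots for seven tests, and this summary: "Descriptive statistics of raw data and change from baseline data will be provided by treatment group for each scheduled time". For vital signs it plans listings and this: "Descriptive statistics will be provided for raw data and absolute change from baseline by scheduled time for each treatment group". SAP 4.1.5 defines descriptive statistics for quantitative data as N, mean, SD, "standard error of the mean (SEM), median, minimum and maximum". Qualitative results get frequencies and percentages.

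Two kinds of value are left out of these summaries. SAP 4.1.5 sends unscheduled assessments to listings, apart from those used as baseline. For vital signs the SAP adds: "Post-dose recheck values will not be used for calculation of descriptive statistics".

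Protocol 14.5 says that the SAP will indicate deviations from the protocol's analyses. SAP Section 5 lists five modifications, and the shift tables are not among them.

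**The concern.** Changes in laboratory parameters are a component of the Part 1 primary endpoint and of a Part 2 secondary endpoint. In cohorts of 6 and arms of 20, a safety signal is likely to be one or a few patients. The useful question is how many patients left their baseline category and how far they went. A shift table answers that; statistics by visit do not.

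The adverse event tables do not fully fill the gap. Protocol 13.1.1 says that abnormal laboratory findings "should not be reported as AEs unless they are associated with clinical signs and symptoms, lead to treatment discontinuation, or are otherwise considered clinically relevant". That judgement is the investigator's. The SAP's CTCAE-grade tables cover treatment-emergent adverse events only. A marked but symptom-free value that the investigator judges not clinically relevant therefore enters no patient count. The protocol itself takes such values seriously: the dose-limiting toxicity definition in 10.2 covers "An AE, injection site reaction, laboratory parameter abnormality, or vital sign abnormality, possibly or probably related to study drug", naming laboratory and vital-sign abnormalities alongside adverse events.

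**Working it through.** The point rests on a comparison of texts. The plan states no figure to reproduce.

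**Step 1. Commitment against plan.**
- Change from baseline over time: promised in protocol 14.2.5; planned in SAP 4.10.2 and Vital Signs.
- Shift tables for selected laboratory parameters and vital signs: promised in protocol 14.2.5 and the synopsis; planned nowhere in the SAP. The protocol leaves the selection of parameters open and the SAP makes none.
- Declaration of the change: called for by protocol 14.5; absent from SAP Section 5, which does record the renaming of the safety population.

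**Step 2. Where a severe laboratory value not recorded as an adverse event would appear.**
- Taken at a scheduled visit: in the listing, and as that visit's minimum or maximum in its arm or cohort, with no patient attached.
- Taken at an unscheduled post-baseline visit: in the listing only.

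**Step 3. What the visit statistics can and cannot show.** The values here are assumptions for illustration. Take a Part 2 arm of 20 with every baseline creatine kinase at 0.6 x ULN. At each of Days 43, 64 and 85, 19 patients are at 0.6 x ULN and one is at 10 x ULN. Then at each visit:
- mean = (19 x 0.6 + 10)/20 = 21.4/20 = 1.07 x ULN
- median = 0.6 x ULN
- maximum = 10 x ULN
- largest change from baseline = 10 - 0.6 = 9.4 x ULN

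So the extreme value is visible. Now compare two cases:
- Case A: the same patient has the high value at all three visits. Patients affected: 1/20 = 5%.
- Case B: three different patients have it, one at each visit. Patients affected: 3/20 = 15%.

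Each visit's set of values is the same in both cases, so every planned statistic, raw and change, is identical. A shift to worst post-baseline category separates them. The result does not depend on the assumed height: at 3 x ULN the mean is (11.4 + 3)/20 = 0.72, and at 20 x ULN it is (11.4 + 20)/20 = 1.57. The median stays at 0.6 and the maximum equals the assumed value.

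If the 10 x ULN value came only from an unscheduled sample and all scheduled values were 0.6, the table's mean, median and maximum would all be 0.6 x ULN.

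**The case against.** The strongest reply is that little is hidden. The planned tables give the median, minimum and maximum, every individual laboratory value is listed, and with 6 or 20 patients a reader can work through the listings. This is right as far as it goes. A reader might infer that the SAP reports only means, or that a severe laboratory value not called an adverse event appears in no safety table. SAP 4.1.5 supports neither inference. What remains missing is the count of patients and their baseline category, and any summary of unscheduled laboratory values.

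Second, the adverse event route is wider than it may look. Protocol 13.4 requires clinically relevant laboratory changes to be recorded as adverse events. The only causality assessment described (13.3) is for adverse events, so it is an inference that a dose-limiting laboratory abnormality could exist without an adverse event record. The Safety Review Team also sees laboratory and vital-sign data directly. This narrows the gap to values judged not clinically relevant. It does not supply the promised table, because review during the trial is not a reported result.

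Third, one might infer that the protocol's commitment to summarize overall toxicity by grade was also dropped. That sentence follows the adverse event sentences, and the SAP's tables of treatment-emergent events by CTCAE grade plausibly meet it. The recheck exclusion, too, is stated for vital signs and ECG, not for laboratory tests.

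Finally, the SAP allows additional analyses as appropriate. An option of that kind does not replace a specific commitment.

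**Conclusion.** The concern holds as an undeclared omission with a limited consequence. Followed as written, the SAP produces no table counting patients whose laboratory values or vital signs move from normal to abnormal or to a higher grade. Frequencies for qualitative tests such as the dipstick give counts by visit, but do not link them to baseline. For a laboratory value not recorded as an adverse event, the reader has an unattributed extreme at a scheduled visit, or a listing entry if the sample was unscheduled.

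The size cannot be given as an error in any estimate. It is the loss of counts in which one patient is 1/20 (5%) of a Part 2 arm or 1/6 (about 17%) of a Part 1 cohort. How often such values occur is not known from the documents. The conclusion assumes only that the SAP is carried out as worded and that its optional analyses are not relied on. It does not affect the efficacy or pharmacodynamic analyses. It should be corrected before database lock.

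**What to change.** In SAP 4.10.2 and Vital Signs, restore the shift tables and name the parameters. A workable set is CK, myoglobin, aldolase, AST, ALT, creatinine, glucose, hemoglobin, platelets and the vital signs. Tabulate baseline category against worst post-baseline category, using CTCAE grade where one exists and low/normal/high otherwise, by cohort in Part 1 and by treatment group in Part 2. State the limits for vital signs, since neither document gives any. For the comparison with placebo, take the worst value within the double-blind period, because all patients who continue receive ACE-083 from Day 190.

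Include unscheduled laboratory values and vital-sign rechecks when deriving the worst value, and write this as an exception to the exclusions in SAP 4.1.5 and Vital Signs. The protocol does not itself require worst-value or CTCAE-grade shifts; these are recommended so that the tables catch the values now confined to listings.

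The minimum alternative is to declare and justify the removal in SAP Section 5. That settles the inconsistency but leaves the counts missing.

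The cost is SAP wording and a few standard tables from data already collected. The downside is that some isolated abnormalities judged not clinically relevant will be shown.

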#### Vital Signs

Individual vital sign data will be listed.

Vital sign parameters consist of weight, heart rate, systolic and diastolic blood pressure.

Descriptive statistics will be provided for raw data and absolute change from baseline by scheduled time for each treatment group. Post-dose recheck values will not be used for calculation of descriptive statistics.

Additional analyses may be performed as appropriate.

#### Electrocardiogram

Individual twelve-lead electrocardiogram (ECG) data will be listed and consists of the following: heart rate, PR, QRS, QT, and QTcB (Bazett correction).

Descriptive statistics will be provided for raw data and absolute change from baseline by scheduled time for each treatment group. Post-dose recheck values will not be used for calculation of descriptive statistics.

Additional analyses may be performed as appropriate.

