¹ Study procedures must be done prior to administration of study drug. Reference the Study Manual for the order of study procedures. Laboratory samples and functional/strength assessments may be collected up to 24 hours prior to administration of study drug. All visit-day windows should be considered relative to the date of the previous dose of ACE-083. Actual visit days (e.g., Day 1, Day 8, Day 22) may be different than planned due to windows on visits and potential dosing delays. Time of study drug administration is the time of the first injection.

² Patients who discontinue prior to the Day 358/ET visit should complete the Day 358/ET visit at the time of discontinuation and return for the remaining follow-up period visit. If an MRI has been completed within 4 weeks of discontinuation, it does not need to be repeated as part of the Day 358/ET visit procedures.

³ Pregnancy test for women of childbearing potential to be performed and negative result confirmed before dosing.

⁴ Includes knee extension, ankle dorsiflexion, and ankle plantarflexion.

⁵ To be performed at screening if patient has not already had testing performed previously.

⁶ Full physical examination includes skin, head, eyes, ears, nose, throat and neck, lymph nodes, cardiovascular, respiratory, gastrointestinal, musculoskeletal, and neurological

⁷ Limited physical examination includes skin, cardiovascular, respiratory, musculoskeletal and neurological assessments

⁸ Injection site examination including but not limited to evaluating erythema, pain, bruising, bleeding, and other signs of discomfort or skin reaction to be completed at least 30 minutes after injection.

⁹ Vital signs (weight, heart rate, systolic and diastolic blood pressure) must be taken prior to administration of study drug on dosing days. Height is collected only at screening.

¹⁰ Tests defined in Appendix 2, Table 7.

¹¹ Including but not limited to: insulin-like growth factor-1 (IGF-1) and serum C-terminal collagen crosslinks (CTX)

¹² If a patient has a positive ADA result at Day 393/EOS, the patient will be asked to return to the clinical site for additional follow-up approximately every 3 months until a negative or stable result is obtained.

¹³ PK samples on a dosing day have a ±15 minute window for post-dose sample collection, based on the time of the first injection. Pre-dose samples may be collected up to 4 hours prior to dosing.

¹⁴ ECG is to be conducted ± 1 hour of the 4h PK sample.

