**4.1.4. Definitions of Baseline****Part 1 and Part 2 (Double-blind Phase)**

Baseline is defined to be the last non-missing assessment prior to the first dose of study drug administration. Theoretically, this could be either the Screening assessment or the Day 1 assessment depending on the parameter.

The first dose date will serve as the reference from which the non-missing pre-treatment values would be identified. For patients that are randomized (applicable to patients participating in Part 2) but do not receive any study drug administration, the date of randomization will be the baseline reference.

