 PK samples on dosing day have a ±15 minute window for post-dose sample collection. Pre-dose samples may be collected up to 4 hours prior to dosing.

 ECG is to be conducted within 1 hour of the 4h PK sample.

 MRI assessments should be completed within 5 days prior to the scheduled dose administration, with the exception of the Day 1 MRI which may be completed within 14 days prior to Day 1 visit. MRI assessments during the follow-up period (Day 358/ET and Day 393/EOS) have a ± 5 day window.

 10-meter walk/run, 6-minute walk. Tests may be performed within 3 days prior to Day 1 visit.

 Gait parameters, Berg balance scale. Tests may be performed within 3 days prior to Day 1 visit.

 Maximum voluntary isometric contraction testing will be conducted using a handheld dynamometer. Both sides will be tested (right and left).

 CMTES2 to be assessed by investigator; CMT-HI to be completed by patient

 Randomization should occur within 24 hours of Day 1 dose.

 PAMSys™ device is a physical activity monitoring system that will be worn by the patient for the duration of the study.

 Study drug administration should occur within 21 days (± 3 days) of the previous dose.

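### SAP 4.10.2 plans Bazett as the only QT correction, so in Part 2 the change from a screening ECG to a 4-hour post-dose ECG can carry a heart-rate artefact; adding QTcF beside it costs almost nothing

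*SAP*

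**What the plan says.** The SAP's Electrocardiogram text (under 4.10.2) says that individual 12-lead data will be listed, and names the variables as "heart rate, PR, QRS, QT, and QTcB (Bazett correction". The analysis is descriptive: "Descriptive statistics will be provided for raw data and absolute change from baseline by scheduled time for each treatment group". Protocol 14.2.5 is consistent with this and names no correction: "Change from baseline in clinical laboratory parameters, ECG, and vital signs will be summarized across time". SAP Section 5, which lists departures from the protocol's statistical section, does not mention ECG.

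SAP 4.1.4 sets the reference value: "Baseline is defined to be the last non-missing assessment prior to the first dose of study drug administration". In the Part 2 schedules (Protocol Table 6 and SAP Appendix 1) ECGs fall at screening (Day -28 to -7), 4 hours after Dose 1 (Day 1) and 4 hours after Dose 5 (Day 85). The timing footnotes agree: "ECG is to be conducted ± 1 hour of the 4h PK sample" in the protocol and "ECG is to be conducted within 1 hour of the 4h PK sample" in the SAP. Part 1 schedules a single ECG, on Day 1.

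**The concern.** Bazett's formula divides QT by the square root of the RR interval. It removes the influence of heart rate only if QT really varies as the square root of RR. If the true relation is flatter, QTcB rises when heart rate rises and falls when heart rate falls, with no change in repolarisation.

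The Part 2 schedule gives heart rate room to differ. The only scheduled pre-dose ECG is at screening, and no pre-dose ECG is scheduled on either dosing day. Every scheduled change therefore compares a screening visit with a time point about 4 hours after injections into both legs. For Day 85 the gap is roughly 13 to 16 weeks: (85 + 7)/7 = 13.1 and (85 + 28)/7 = 16.1.

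At stake is the reading of the only corrected repolarisation summary in the plan. A within-arm QTcB change could be partly or wholly a heart-rate effect, or a real change could be offset by one.

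**Working it through.** The documents state no QT figure, QTc threshold or ECG sample size, so there is no figure of the plan's own to reproduce. The check has two parts.

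**1. What is compared.** Under SAP 4.1.4, baseline is the last non-missing pre-dose value. In Part 2 the scheduled value that qualifies is the screening ECG; the Day 1 and Day 85 ECGs are both post-dose. In Part 1 the single scheduled ECG gives no scheduled change from baseline.

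**2. How large the artefact could be.** All inputs here are assumptions, because the documents give no heart rates, QT levels or QT-RR exponent.

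- RR = 60/HR, in seconds.
- QT = 400 × RR^e ms, with no true repolarisation change.
- QTcB = QT/RR^(1/2); QTcF = QT/RR^(1/3).

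*Heart rate 60 to 70 bpm.* RR goes from 1 to 60/70 = 0.857. At 60 bpm, QT, QTcB and QTcF are all 400 ms.

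| True exponent e | QT at 70 bpm (ms) | Change in QTcB (ms) | Change in QTcF (ms) |
|---|---|---|---|
| 1/3 | 400 × 0.857^(1/3) = 380.0 | +10.4 | 0.0 |
| 0.4 | 400 × 0.857^0.4 = 376.1 | +6.2 | -4.1 |
| 0.5 | 400 × 0.857^0.5 = 370.3 | 0.0 | -10.1 |

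*Heart rate 65 to 75 bpm, wider range of exponents.*

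| True exponent e | Change in QTcB (ms) | Change in QTcF (ms) |
|---|---|---|
| 0.25 | +14.9 | +4.8 |
| 0.30 | +11.8 | +1.9 |
| 1/3 | +9.8 | 0.0 |
| 0.40 | +5.8 | -3.8 |
| 0.45 | +2.9 | -6.6 |
| 0.50 | 0.0 | -9.3 |

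*Other heart-rate changes, e = 1/3, screening rates of 60 to 75 bpm.* A rise of 5 bpm shifts QTcB by +4.5 to +5.4 ms, and a rise of 15 bpm by +12.8 to +15.2 ms. A fall of 5 bpm shifts it by -4.7 to -5.8 ms, and a fall of 15 bpm by -15.2 to -18.7 ms.

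*Masking.* Take e = 1/3, a true lengthening of 10 ms (400 to 410) and heart rate falling from 75 to 65 bpm. QTcB goes from 415.2 to 415.5 ms, a change of +0.3 ms. QTcF shows +10.0 ms.

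*Uncorrected QT.* With e = 1/3 and no true effect, raw QT shifts by -18.1 ms from 65 to 75 bpm, so it cannot stand in for a second correction.

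Three things follow. QTcB is free of the artefact only at exponent 0.5, and QTcF only at 1/3. Between those values the two err in opposite directions and bracket the true change; below 1/3 they err in the same direction, QTcF by less. In the second table the gap between the two columns is 9.3 to 10.1 ms whatever the exponent. It measures how far the result depends on the choice of correction, and does not show which correction is right.

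**The case against.** The case for leaving the SAP alone is substantial.

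- **The data to resolve it are there.** Heart rate, QT and QTcB are listed per patient, so another correction can be derived later. This stands.
- **The warning sign is already tabulated.** Heart rate from the same ECGs is summarised as raw values and change from baseline, by time and arm, so a mean shift would be visible beside QTcB. This stands, although separate means of QT and heart rate do not give the mean or spread of corrected changes, which are nonlinear and paired within patient.
- **Placebo controls the setting.** Both arms have the same ECG schedule, so a shift due to visit conditions or time of day is expected in both. This stands for the arm comparison. It does not cover a drug effect on heart rate; the documents report none, and Protocol 5.1 describes a drug that stays mainly in the injected muscle.
- **Nothing formal depends on it.** ECG has no test, QTc threshold or stopping rule attached. This stands.
- **The SAP allows additional analyses.** It does, but that leaves the second correction to be chosen after results are seen, whereas SAP Section 1 gives pre-specification before database lock as the SAP's purpose.

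A reader might infer that a QT signal in this trial could never be told apart from a correction artefact. The documents do not support that, given the listings, the heart-rate summary and the placebo arm. A reader might also infer that reporting both corrections always brackets the truth. The rows for exponents 0.25 and 0.30 show otherwise.

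**Conclusion.** The point holds as a minor improvement to a descriptive safety summary in Part 2. QTcB is the only corrected QT planned, and each scheduled change compares screening with 4 hours post-dose. If heart rate differs between the two and the true exponent is not 0.5, the planned QTcB change is shifted. Under the illustrative assumptions (QT 400 ms at 60 bpm, a 10 bpm rise) the shift runs from 0 ms at exponent 0.5 to +10.4 ms at 1/3. Those values are not trial data, and nothing in the documents says whether heart rate will differ or what the exponent is.

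What remains exposed in the planned tables is the within-arm change and, if the drug alters heart rate, the arm difference. The plan contains no contradiction here, and the primary analysis and sample size are unaffected. Part 1 is outside the point.

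**What to change.** In the Electrocardiogram text of SAP 4.10.2, add QTcF = QT/RR^(1/3), with RR = 60/heart rate, to the listed variables and to the raw and change-from-baseline summaries beside QTcB. State that both are to be read with the heart-rate change from the same ECGs, and that neither is assumed to be free of bias. Keep QTcB. Make the change before unblinding, so that the second correction is not chosen in response to the results.

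The cost is one derived variable, one listing column and one extra row per ECG table. It needs no new data, visit or procedure.
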